2.2 Study objective

2.2.1 Primary objective

To demonstrate that treatment with the ClariFix cryotherapy device is superior to a sham treatment in patients with chronic rhinitis.

2.2.2 Secondary objectives

- To demonstrate durability of the treatment effect through 365 days of follow-up.
- To support peer-reviewed publications on the ClariFix technology.

2.3 Study endpoints

2.3.1 Primary endpoint

The primary endpoint is the percentage of responders at 90 days. Responders are defined as participants with a 30% or greater reduction in rTNSS relative to baseline. The active treatment group will be compared with the sham-control group.

2.3.2 Secondary endpoints

The following secondary endpoints will compare the active treatment group with the sham-control group at 30-day and 90-day follow-ups:

- Mean change from baseline in rTNSS score
- Mean change from baseline in Standardized Rhinoconjunctivitis Quality of Life Questionnaire (RQLQ(S)) score
- Mean change from baseline in EuroQol 5-dimension survey (EQ-5D-5L) scores
- Percent of patient satisfaction at follow-up
- Rate of serious device- or procedure-related adverse events (SAEs)

The following secondary endpoints will be assessed at all follow-ups for all participants who receive active treatment (randomized or crossover):

- The percentage of responders
- The mean change from baseline in rTNSS score
- The mean change from baseline in RQLQ(S) score
- Mean change from baseline in EQ-5D-5L scores
- Percent of patient satisfaction at follow-up

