2.10.4 Randomization and blinding

Randomization assignments will be generated by in independent statistician using variable block size distribution by site with a 1:1 allocation to active or sham treatment. Randomization will also be stratified by allergy subgroup (allergic, nonallergic). The randomization schedule will be entered into the Medrio electronic data collection (EDC) randomization module. Randomization will occur on the day of the procedure and after all baseline data have been collected and eligibility has been confirmed. All randomized and treated participants will be considered enrolled. Confirmation of randomization assignment from EDC will be printed and filed in the study record.

This is a single-blind study; participants will be blinded to the randomized assignment. To facilitate blinding, control participants will undergo a sham procedure using the ClariFix device without a cryogen cannister. To support blinding, participants will wear blindfolds during the procedure to limit any visual clues that may suggest the treatment assignment. A separate device with a canister held near the participant will be used to provide the sound of the gas release from the cannister. A standardized script for the physician/staff will be used during the procedure to assure blinding. Additionally, local anesthesia regimes will be the same for both treatment groups within each investigational center.

Participants will complete a blinding questionnaire at completion of the procedure and at the 30-day and 90-day follow-up visits to assess the adequacy of the blinding procedures. Upon

completion of their 90-day visit, each participant will be unblinded. Sham control participants will be offered the opportunity to receive active treatment if they wish and still meet eligibility criteria.

Before the 90-day visit, unblinding of participants will only occur when medically necessary. In the event of a device-or procedure-related SAE, the sponsor may authorize the site to unblind the participant in order to adequately assess the event.

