2.10.5 Procedure (Active and Sham)

Pregnancy testing

Before the procedure, urine pregnancy tests are required for all women of childbearing potential. In the case of pregnancy, use medical judgement to select appropriate procedural anesthesia medications (eg, low doses of epinephrine and lidocaine) that are safe for use during pregnancy.

Procedure anesthesia

The local anesthesia regimen for the procedure for both active and sham treatments will be performed according to the physician's usual practice. Information regarding the anesthesia regimen will be documented in the study records.

Study procedure

Below is a high-level description of the procedure for both the active and sham procedures. Detailed instructions on the preparation, usage, and storage of the ClariFix device is available in the instructions for use (packaged with the device). To maintain the participant blind during the procedure, the sham devices will be identical to the active devices except the cryogen cannister will not be inserted into the device.

- 1) Review and update concomitant medications.
- 2) Perform quantitative endoscopic rhinoscopy before administration of nasal decongestant to evaluate nasal congestion.
- 3) Administer decongestant. If the participant is a woman of childbearing potential, use medical judgement to select a decongestant (eg, oxymetazoline) that is safe to use during pregnancy.
- 4) Perform quantitative endoscopic rhinoscopy to assess degree/extent of rhinorrhea and postdecongestant nasal congestion, and plan target treatment placement at the middle meatus.
- 5) Administer local anesthesia to both sides of the nasal cavity.
- 6) Have the participant put on the blindfold.
- 7) Prepare the ClariFix device according to the IFU (for sham treatment, do not insert the cryogen cannister).
- 8) Place the cryoprobe in firm contact with the targeted middle meatus tissue under visual guidance.

- 9) For active treatment: initiate the flow of cryogen for a total of 30 seconds and, using endoscopic visualization, ensure the cryoprobe is functioning.

 For sham treatment: turn on the device and leave the cryoprobe in contact with tissue for the 30 seconds, tissue will not freeze with the sham treatment. Use a separate device held near the participant to provide the sound of gas release from the cannister.

 For both treatments, during this time, instruct the participant breathe in and out through their mouth.

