The EQ-5D-5L will be completed at baseline and all follow-up visits. The mean change from baseline in the EQ-5D-5L will be evaluated and compared between treatment groups as a secondary endpoint at the 30-day and 90-day follow-up periods. Additionally, the mean change from baseline will be accessed at all follow-ups for all participants who received active treatment (randomized or crossover).

Satisfaction questionnaire

The satisfaction questionnaire consists of 3 questions that the participant answers at each follow-up visit. The questions indicate whether the participant is satisfied with the procedure outcome, whether the participant would undergo the procedure again for similar results, and whether the participant would recommend the procedure to family or friends with a similar condition. For each item the participant indicates agreement/disagreement with each statement.

Serious device- or procedure-related adverse events (SAEs)

The rate of serious device- or procedure-related adverse events (SAEs) will be compared between treatment groups through the 90-day follow-up visit (**Section 6**). The parameter of interest is the percent of participants who experience 1 or more device- and/or procedure-related SAEs from the time of the index procedure through the 90-day follow-up.

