6.2 Assessing, recording, and reporting of adverse events

For the purposes of this study, all serious adverse events (regardless of relationship) must be reported. Only nonserious adverse events that are related to the device, procedure, or the participant's ENT condition(s) should be reported. Nonserious adverse events that are not related to the device, procedure, or ENT conditions should not be reported.

An adverse event may be volunteered spontaneously by the participant or discovered by the investigator or study staff upon questioning or physical examination of the participant. The following information should be reported for all reportable adverse events and updated as needed until the event resolves:

- Adverse event (diagnosis associated with the main complaints or symptoms)
- Date the adverse event occurred
- Date the investigator (or staff) became aware of the adverse event

- Adverse event details (main complaints or symptoms)
- Relationship to study device
- Relationship to the study procedure
- Seriousness of the adverse event.
- Interventions undertaken
- Status of the adverse event (ongoing, resolved, unresolved but stable, death)
- Date of event resolution, if applicable

Source documents (eg, procedural notes, treatment notes, clinical summary) may be required as supporting documentation for an adverse event.

Any serious device- or procedure-related adverse events should be reported to the sponsor as soon as possible (preferably within 24 hours) after the investigator or clinic staff become aware of the event. Initial report of the event can be by email and/or telephone call to a sponsor representative.

During the study, **all** participant deaths must be reported to the sponsor within **24 hours** of the investigator's (or designated staff's) knowledge of the death. Deaths should be reported as the reason for study exit and the cause of the death should be reported as an adverse event. A copy of death records, medical records for the event(s) that led to the participant's death, death certificate (if available), and an autopsy report (if performed) should be deidentified and sent to the sponsor as soon as they become available for any death deemed related to the device and/or procedure.

7 Protocol Deviations

Investigators are required to adhere to the study protocol, applicable national or local laws and regulations, and any conditions required by the applicable IRB or regulatory authority.

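### The only listed between-arm safety endpoint rests on a relatedness judgement that is probably not masked to arm; all-cause SAEs by arm should stand beside it

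*Combined protocol and SAP*

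**What the plan says.** - **Endpoint.** Section 2.3.2 lists five secondary comparisons of active with sham. The only one about safety is "Rate of serious device- or procedure-related adverse events (SAEs". Section 2.11.2 defines it: "The parameter of interest is the percent of participants who experience 1 or more device- and/or procedure-related SAEs", counted from the index procedure to the 90-day follow-up. Section 2.7 puts secondary endpoints under a 2-sided 0.05 test, so this is a planned comparison and not only a listing.
- **Collection.** Section 6.2 takes in every SAE: "serious adverse events (regardless of relationship) must be reported". Nonserious events are filtered at entry: "Nonserious adverse events that are not related to the device, procedure, or ENT conditions should not be reported". The event report has a field "Relationship to study device" and a matching one for the procedure. The section does not say who completes them.
- **Blinding.** Section 2.10.4: "This is a single-blind study; participants will be blinded to the randomized assignment". The same section adds: "Confirmation of randomization assignment from EDC will be printed and filed in the study record". The operator prepares the device knowing the arm (2.10.5: "for sham treatment, do not insert the cryogen cannister"). The document describes no events committee, masked assessor or written causality criteria.

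**The concern.** Randomization balances how often serious events occur in the two arms. It does not balance a later causality judgement made by someone who knows the arm. If the same event is more readily called related after a freeze than after a sham, or the reverse, the endpoint partly compares attribution habits. A spurious excess could appear, or a real one could be understated.

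SAEs are the one class of event that the protocol collects with no relationship filter. The endpoint then applies such a filter, so no listed between-arm safety comparison is free of a relatedness judgement.

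**Working it through.** **1. Is there a plan figure to reproduce?** Not for this endpoint: no expected rate, power or margin is given. The sample size in section 2.6 concerns the primary endpoint only. With 73.5% v 45%, 1-sided 0.025, 90% power and a mean proportion of 0.5925:

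n = [1.960 × √(2 × 0.5925 × 0.4075) + 1.2816 × √(0.735 × 0.265 + 0.45 × 0.55)]² / 0.285² = (1.362 + 0.852)² / 0.0812 ≈ 60.4, so 61 per arm.

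This agrees with the plan and is unaffected by the point. Enrollment of 128 at 1:1 gives 64 per arm, used below.

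**2. Which events are open to differential attribution?**

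- *Shared by both arms (2.10.5):* decongestant, local anesthesia, endoscopy, and probe contact for 30 seconds plus at least 60 more. An event arising from these can be called procedure-related in either arm.
- *Active only:* the freeze.
- *Overlap in the risk lists (3.2):* bleeding appears under both rhinoscopy and cryosurgery; headache and infection appear under both anesthesia and cryosurgery.

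The exposed events are therefore those that could be read as a cold effect by someone who knows that a freeze took place, and as background by someone who knows that none did.

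**3. How many events are at issue?** The pilot (1.2) reported no related SAEs in 27 participants. The exact upper 95% limit is 1 − 0.025^(1/27) = 12.8%, so this is weak evidence of a low rate. The documents give no all-cause SAE rate. The table assumes the same true all-cause risk in both arms. Expected related count = 64 × risk × share called related.

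| Assumed all-cause risk | All-cause participants per arm | Related, active v sham: shares 50% v 50% | 80% v 20% | 20% v 80% |
|---|---|---|---|---|
| 1% | 0.64 | 0.32 v 0.32 | 0.51 v 0.13 | 0.13 v 0.51 |
| 3% | 1.92 | 0.96 v 0.96 | 1.54 v 0.38 | 0.38 v 1.54 |
| 5% | 3.20 | 1.60 v 1.60 | 2.56 v 0.64 | 0.64 v 2.56 |

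Even with the strong 80/20 split, the artefact at 3% is 1.54 − 0.38 = 1.2 participants. The all-cause column does not change with attribution.

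**4. What does one decision do?** Each attribution decision moves an arm's rate by 1/64 = 1.6 percentage points. Suppose two participants per arm have an SAE. All-cause, this is 2 v 2. Depending on attribution alone, the related count can run from 2 v 0 to 0 v 2.

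**5. Could a test settle it?** Section 2.7 names no test for this endpoint; a two-sided Fisher exact test is assumed here. For k v 0 at 64 per arm, p = 2 × C(64,k)/C(128,k): 2 v 0 gives 0.496, 5 v 0 gives 0.058 and 6 v 0 gives 0.028. Exact power is 0.7% for 3% v 1%, 5.8% for 5% v 1%, and 31% for 10% v 2%. With 0 of 64, the upper 95% limit is 1 − 0.025^(1/64) = 5.6%. The endpoint will be read from counts and intervals, which is where attribution shows.

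**The case against.** **Who assigns relatedness is not stated.** A reader might infer that the protocol gives causality to an investigator who knows the arm. Section 6.2 only lists the fields. An arm-aware assessor is the likely reading of site-level reporting in a single-blind trial, but it remains an inference. This objection stands, and the conclusion is worded accordingly.

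**Sham events can count.** A reader might infer that the sham rate is close to zero by construction, since a device without cryogen can hardly cause harm. The endpoint also takes procedure-related SAEs, and sham participants undergo the same anesthesia, endoscopy and probe contact. This stands and narrows the concern to events that might be read as freeze effects.

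**The data will exist.** A reader might infer that a difference between arms could never be separated from attribution. Because all SAEs are collected, the separation can still be made at reporting. Section 2.3.3 also leaves exploratory outcomes to a Statistical Analysis Plan whose text was not supplied, and an all-SAE table there cannot be ruled out. That would meet much of the point, although it would not alter the endpoint defined in 2.3.2 and 2.11.2.

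**Little depends on it.** The endpoint is secondary, has no margin or success criterion, and expects few events. This stands and limits the weight of the point.

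**All-cause counting has its own weaknesses.** It adds unrelated events to a sparse outcome. Seriousness is also a judgement, since section 6.1 includes important medical events, and site staff make it. Both are true, and both argue for adding the all-cause line and not for substituting it.

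**Conclusion.** The concern holds in limited form. The only listed between-arm safety endpoint passes through a relatedness judgement with no described masking, while the attribution-free count is already collected and is not among the listed comparisons.

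The likely distortion is about one participant per arm at assumed all-cause risks of 1% to 5%, in either direction. Any ratio of apparent rates, such as fourfold for an 80/20 split, simply restates the assumed shares and is not evidence of bias in this trial. The documents do not show that attribution will differ by arm; they show only that nothing described prevents it. The primary analysis and sample size are untouched.

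The conclusion rests on two assumptions: that relatedness is assigned at the site by staff aware of the arm, and that no all-SAE comparison is planned in an SAP outside the supplied text.

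**What to change.** In sections 2.3.2 and 2.11.2:

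1. Keep the related-SAE endpoint, and add beside it the percent of randomized and treated participants with at least one SAE of any cause from the index procedure through the 90-day visit. Present it by arm with counts and a risk difference with 95% CI. The denominator matches sections 2.7 and 2.10.4, under which those randomized but not treated are not considered enrolled; they also have no index procedure to count from.
2. Label the related-SAE line as attributed without masking to arm.

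If a separate SAP already contains an all-SAE comparison by arm, a cross-reference and the label suffice.

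**Cost.** Wording and one table row. No new data are needed, because section 6.2 already requires all SAEs. The downsides are some noise from unrelated SAEs and a judgement of seriousness that remains unblinded.

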2.3.3 Exploratory endpoints

Additional exploratory outcomes will be detailed in the Statistical Analysis Plan.

2.4 Study size and duration

The study will be conducted at up to 12 investigational centers in the US.

A sufficient number of participants will be screened and consented to reach a total enrollment of 128 participants. Enrollment in the study is anticipated to take approximately 12 months. Participants are considered enrolled at the time of randomization and procedure.

The expected duration of study participation is 13 months for active treatment participants and 16 months for sham-control participants who chose to crossover to active treatment. There is a maximum of a 30-day screening period for all participants. Postprocedure follow-up for active treatment participants is 365 days (12 months). Sham-control participants who meet the criteria may crossover to active treatment after their 90-day follow-up and then complete the same full 365-day postprocedure follow-up as the active participants. Those sham-control participants who

do not meet the original inclusion/exclusion criteria at the 90-day follow-up or elect not to crossover to the active treatment will be exited from the study after their 90-day follow-up.

2.5 Study hypothesis

The primary endpoint is the percentage of participants in each arm who achieve an improvement ≥30% in total rTNSS score at 90 days compared with baseline. The primary endpoint will be compared between treatment groups for superiority of active to sham treatment by testing the following 1-sided hypotheses using the Z-test of 2 proportions:

 H_0 : $p_{ClariFix} \le p_{sham}$

versus

 H_A : $p_{ClariFix} > p_{sham}$

where $p_{ClariFix}$ and p_{sham} are the percentages of responders in the active ClariFix and sham groups, respectively.

2.6 Sample size estimation

The sample size was calculated using PASS 16 Power Analysis and Sample Size Software (2018), NCSS, LLC., Kaysville, Utah, USA (ncss.com/software/pass). The sample size was calculated with 90% power and a 2.5% 1-sided type 1 error rate based on the following assumptions:

- 1:1 randomization allocation
- Percent of rTNSS responders in active treatment group = 73.5% (95% CI, 63.6% to 81.9%)
- Percent of rTNSS responders in sham control group = 45%

The active response rate is based on the 90-day response rate in FROST. ¹² The sham control group rate is based on the placebo rate reported by Benninger et al for a systematic review of rhinitis pharmaceutical studies. ¹³ In the drug trials evaluated, they reported mean placebo reponse rates of -15.0% (range -7.6% to -40.0%) at 2-week follow-up for seasonal allergic rhinitis and -24.8% (range -14.4% to -37.2%) at 4- to 6-week follow-up for perennial allergic rhinitis. To ensure adequate sample size, the anticipated placebo rate was slightly overestimated from these values.

Additionally, powering the sample size for subgroup analysis of allergic vs nonallergic participant rTNSS responses was considered. However, data from the FROST study (**Table 1**)¹² indicated that there is no difference in response rates between allergic and nonallergic patients and that the groups are poolable at the 90-day follow-up period, so enrollment by allergy subgroup was not incorporated into the sample size calculation. An assessment of poolability by allergy subgroup will be performed during analysis.

Table 1. FROST 90-Day Total rTNSS Responder Rate by Allergy Subgroups

Group	Improved ≥30%
Allergic	73.3% (22/30)
Nonallergic	73.5% (50/68)

Under the assumptions outlined above, a total sample size of 122 randomized participants (61 per arm) is adequate to test this hypothesis. To account for approximately 5% attrition at 90 days, a total of 128 participants will be enrolled in the study.

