1.2 Report of prior investigations

A pilot clinical study was performed at 3 investigational sites in the US to evaluate the performance of the ClariFix device as a cryosurgical tool to treat patients with chronic rhinitis. This study was a prospective, multicenter, single-arm interventional, nonsignificant risk study of the ClariFix device.

A total of 27 participants were enrolled and bilateral treatments were successfully completed with no complications in 100% of participants using injected or topical anesthesia in the office. All participants completed the 30-day follow-up and 24 of the 27 participants (88.9%) completed the 90-day follow up (3 participants were lost-to-follow-up) and participated in the extended follow-up. Nasal symptoms, assessed by the reflective Total Nasal Symptom Scale (rTNSS), were significantly reduced at each follow-up interval compared with baseline. The average rTNSS score was reduced by 58% from 6.2 at baseline to 2.6 at 30 days and the reduction was maintained at 2.7 at 90 days (56% reduction). Extended follow-up showed sustained improvements: average rTNSS of 2.3 at 180 days post treatment. Eighty-one percent (22/27) of participants had at least a 1-point improvement of rTNSS scores at 30 days and 79% (19/24) of participants had improved rTNSS scores at 90 days. The visual analog scale (VAS) scores similarly demonstrated significant reductions in nasal symptoms. The average total VAS score was reduced by 50% and 53% at 30 and 90 days, respectively. There were no device- or procedure-related serious adverse events (SAEs) reported during the study. This pilot study demonstrated that office-based treatment using the ClariFix device was safe, well-tolerated, and effective in reducing nasal symptoms in participants with chronic rhinitis.

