2.8.1 Inclusion criteria

Study participants MUST meet all of the following criteria:

- 1. Be \geq 21 years of age.
- 2. Has been diagnosed with chronic nonallergic or allergic rhinitis.
- 3. Have moderate to severe symptoms of rhinorrhea (individual rTNSS symptom rating of 2 or 3), mild to severe symptoms of nasal congestion (individual rTNSS symptom rating of 1, 2, or 3), and a minimum total rTNSS score of 4 (out of 12) at baseline.
- 4. Have an allergy test (by skin prick or intradermal testing or by validated *in vitro* tests for specific Immunoglobin E [IgE]) on file within 12 months of the baseline visit.
- 5. Be an appropriate candidate for bilateral ClariFix treatment performed under local anesthesia.
- 6. Be willing and able to comply with all study elements, as indicated by their written informed consent.

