2.8.2 Exclusion criteria

Study participants MUST NOT meet any of the following criteria:

- 1. Have clinically significant anatomic obstructions that, in the investigator's opinion, limit access to the posterior nose, including but not limited to severe septal deviation or perforation, nasal polyps, and/or sinonasal tumor.
- 2. Have had previous sinus or nasal surgery within 6 months of study enrollment.
- 3. Have previously undergone cryotherapy or other surgical interventions for rhinitis.
- 4. Have an active nasal or sinus infection.
- 5. Have rhinitis symptoms that are primarily due to seasonal allergies.
- 6. Have plans to (or otherwise anticipates the need to) undergo an ENT procedure concurrently or within 3 months after the study procedure.
- 7. Is on prescribed anticoagulants (eg, warfarin, Plavix) or 325 mg aspirin that cannot be discontinued before the procedure (81 mg aspirin and herbal supplements are acceptable).
- 8. Be unable to discontinue ipratropium bromide (IB) at least 14 days before baseline and through the 90-day follow-up visit.
- 9. Have a history of chronic epistaxis or experienced a significant epistaxis event (defined as epistaxis event requiring medical intervention) in the past 3 months.
- 10. Have a history of rhinitis medicamentosa.
- 11. Have had previous head and/or neck irradiation.
- 12. Have an allergy or intolerance to local anesthetic agents.
- 13. Have cryoglobulinemia, paroxysmal cold hemoglobinuria, cold urticaria, Raynaud's disease, and/or open and/or infected wounds at or near the target tissue.
- 14. Have a neurological, medical, psychiatric condition, or social circumstance that would potentially increase risk, interfere with study participation, or confound interpretation of study data
- 15. Be participating in another clinical research study.

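### Is the 45% sham responder rate in section 2.6 left without support, so that the 90% power cannot be relied on?

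*Combined protocol and SAP*

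**What the plan says.** Section 2.6 of the combined protocol and SAP sizes the trial for 90% power at a one-sided 2.5% level. The active rate is 73.5%, from the earlier FROST study. The control input is "Percent of rTNSS responders in sham control group = 45" percent. Both rates stand in a list of assumptions, and the resulting 61 per arm is stated to hold under them.

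The support for the control rate is a published review of rhinitis drug trials: "they reported mean placebo reponse rates of -15.0% (range -7.6% to -40.0%) at 2-week follow-up for seasonal allergic rhinitis" and, with a minus sign in front, "24.8% (range -14.4% to -37.2%) at 4- to 6-week follow-up for perennial allergic rhinitis". The section then says: "To ensure adequate sample size, the anticipated placebo rate was slightly overestimated from these values".

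The primary endpoint (section 2.3.1) is the percentage of participants with a reduction of at least 30% in rTNSS at 90 days. Section 2.8.1 admits both disease types: "Has been diagnosed with chronic nonallergic or allergic rhinitis". Section 2.8.2 rules out patients who "Have rhinitis symptoms that are primarily due to seasonal allergies".

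**The concern.** The control rate drives the sample size, and its stated derivation does not hang together, for three reasons.

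- **Scale.** A proportion of responders cannot be negative. A mean percent change in a symptom score can. The minus signs and the word for average suggest the second, and the section gives no conversion to a proportion at the 30% threshold.
- **Wording of the margin.** Read as proportions, the quoted means are 20.2 points (perennial) and 30 points (seasonal) below 45%, which is more than a slight overestimate. Read as mean changes, no margin has been shown at all.
- **Match to the trial.** The figures come from allergic rhinitis, drug placebo and 2 to 6 weeks. The trial uses a sham procedure, measures at 90 days and enrols nonallergic patients, who were 68 of 98 (69%) in FROST. Primarily seasonal disease is excluded.

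The pilot in section 1.2 might also seem to show the two scales diverging, since "the reduction was maintained at 2.7 at 90 days (56% reduction") while "79% (19/24) of participants had improved rTNSS scores at 90 days".

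At stake is whether the 90% power is genuine. If the true sham rate were well above 45%, the trial could miss a real effect, while readers had been told that the input was set cautiously.

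**Working it through.** **1. The plan's own figure.** Inputs from section 2.6: p1 = 0.735, p2 = 0.45, one-sided alpha 0.025 (z = 1.960), power 90% (z = 1.282). With the pooled proportion p = (0.735 + 0.45)/2 = 0.5925:

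n = [1.960 × √(2 × 0.5925 × 0.4075) + 1.282 × √(0.735 × 0.265 + 0.45 × 0.55)]² / (0.735 − 0.45)²

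= [1.960 × 0.6949 + 1.282 × 0.6650]² / 0.0812 = 4.903 / 0.0812 = 60.4

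This rounds up to 61 per arm, or 122 in total, as stated. Enumerating the pooled Z-test over both binomial distributions at 61 per arm gives exact power of 90.7%. The active rate and its interval also reproduce: 72/98 = 73.5%, exact 95% CI 63.6% to 81.9%.

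**2. Quoted figures read as responder rates.** The largest values quoted are 40.0% (seasonal range) and 37.2% (perennial range). The assumed 45% exceeds both. The same formula gives these sizes for 90% power:

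| Sham rate | n per arm |
|---|---|
| 24.8% | 20 |
| 37.2% | 38 |
| 40.0% | 44 |
| 45% (plan) | 61 |

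On this reading the trial is conservatively sized.

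**3. Quoted figures read as mean percent changes.** The documents give no SD. Assume that percent change is normal with an SD of 30 to 50 points. The responder rate is then Φ((mean reduction − 30)/SD). For the perennial mean with SD 40, this is Φ((24.8 − 30)/40) = Φ(−0.13) = 44.8%.

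| Quoted figure | Implied responders (SD 30 to 50) | Exact power at 61 per arm vs 73.5% |
|---|---|---|
| Seasonal mean, 15.0% | 31% to 38% | 98% to 99.9% |
| Perennial mean, 24.8% | 43% to 46% | 89% to 94% |
| Perennial range limit, 37.2% | 56% to 60% | 37% to 54% |
| Seasonal range limit, 40.0% | 58% to 63% | 23% to 44% |

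The conversion is rough. The rTNSS is an integer score, so the reduction actually needed runs from 30% (3 points from a baseline of 10) to 50% (2 points from a baseline of 4). Even so, the perennial mean, which fits the trial best once seasonal disease is excluded, lands on about the 45% assumed.

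**4. Sensitivity, with no SD assumption.** Exact power at 61 per arm against 73.5% active:

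| Sham rate | Power |
|---|---|
| 40% | 97.2% |
| 45% | 90.7% |
| 50% | 77.2% |
| 55% | 57.0% |

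Power falls below 90% at a sham rate of about 45.4% and below 80% at about 49.2%.

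**5. The pilot.** The 56% is the fall in the group mean: (6.2 − 2.7)/6.2 = 0.56. The 79% counts participants who improved; its 30-day counterpart in the same paragraph is defined as a gain of at least one point. Neither is a rate at the 30% threshold, so the contrast says nothing about the trial's endpoint.

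**The case for a change.** The best case for a change is that the design has almost no reserve around the one input whose derivation is missing, yet the section tells readers that a cushion was built in. On the mean-change reading the perennial figure converts to roughly the design value, so no cushion is shown, and the range limits would leave the trial underpowered. Nowhere do the documents give a control rate for a sham procedure, for nonallergic patients or at 90 days. FROST's similar rates by allergy group (73.3% and 73.5%) concern active treatment only. If the trial missed its endpoint, a table of power by sham rate would help to separate no effect from a high sham response.

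Much of this stands. The explanation is incomplete, the sentence about overestimating is loosely worded, and power is steep in the sham rate. What does not follow is that 45% is wrong. That the figures are mean changes is an inference from their signs and label. The range limits are single extremes, and the larger belongs to a disease type that the trial largely excludes. The section already prints the source, indications, follow-up times and ranges, so a reader can see how indirect the evidence is. Section 2.6 also makes the power conditional on the listed assumptions, and anyone can compute the sensitivity table from the stated inputs.

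**Conclusion.** The point is a weakness of documentation, and no change to the plan follows. Given 73.5% and 45%, the 61 per arm is correct and exact power is 90.7%. The documents do not show 45% to be too high or too low. It exceeds every quoted figure if these are rates. It is close to the 43% to 46% implied by the perennial mean if they are mean changes, on the assumption of normality and an SD of 30 to 50 points.

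The real exposure is a sham response above the assumed rate: power would be 77% at 50% and 57% at 55%. Better wording in section 2.6 would not reduce it. The sample size, alpha, test and endpoint would stay the same, and the type I error of the primary comparison does not depend on the planning rate. A sponsor that follows the plan as written reaches the same result. A sentence on what the cited figures measure, or a short sensitivity table, would be a courtesy to readers and is not needed for a sound analysis.
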